**Stanford Neurosurgery**

**Investigator's Agreement**

By signing below I confirm that I have read this protocol and agree that it contains all necessary details for conducting this study. I will conduct the study according to the procedures described in this protocol.

---

Principal Investigator's Signature

---

Date

---

Principal Investigator's Name

---

Principal Investigator's Signature

---

Date

---

Principal Investigator's Name

Site Address:      Stanford University Medical Center  
                          [name]  
                          [name]

*Our study to evaluate peripheral vibrotactile coordinated reset stimulation for Parkinson's disease* seeks to explore the safety and efficacy of an experimental non-invasive method to aid in the symptoms of Parkinson's disease. The purpose of the study is to verify the safety and tolerability of non-painful sensory (tactile) vibratory stimulation delivered to the fingertips of patients with Parkinson's disease.

## **BACKGROUND**

Parkinson's disease

Every year over 50,000 people in the US are diagnosed with Parkinson's disease (PD) and about half a million people have the disease. Because the rate of PD increases in older adults, the burden will increase unless prevention and treatment improve. Current treatments for Parkinson's disease include both medications and surgical measures. Levodopa is still the mainstay of drug therapy in the form of carbidopa/levodopa (Sinemet, Rytary, Duodopa). Additional drugs are available that complement levodopa therapy, including dopamine agonists such as ropinirole (Requip) and pramipexole (Mirapex), COMT inhibitors such as entacapone (Comtan) and tolcapone (Tasmar), anticholinergics such as trihexyphenidyl (Artane) and benztrapine mesylate (Cogentin), MAO inhibitors such as selegiline and amantadine (Symmetrel). Despite the use of these drugs singularly or as combination therapy, none significantly slow the underlying neurodegeneration and many can include intolerable side effects, especially when taken at higher doses as the disease progresses.

Patients with symptoms who become refractory to medication therapy can undergo Deep Brain Stimulation (DBS) surgery. DBS improves symptoms of PD by electrically stimulating brain cells in movement control areas of the brain through chronically implanted electrodes connected to a subcutaneous pulse generator typically placed below the clavicle. However, there are risks associated with this type of operation including risk of stroke, infection, seizure, hemorrhage or others we may not anticipate. Needless to say, less than 10% of surgical candidates for DBS with PD actually undergo the surgery, emphasizing the need for less invasive options.

(<https://report.nih.gov/NIHfactsheets/ViewFactSheet.aspx?csid=109>)

In a previous first in man study five subjects with idiopathic Parkinson's disease were treated with vibrotactile CR stimulation during three consecutive days for 4 h per day (Syrkin-Nikolau et al., 2018) This study demonstrated tolerability as well as feasibility of our method, and revealed a significant improvement of gait and bradykinesia, persisting for at least one month after three days of vibrotactile coordinate reset (CR) stimulation.

Based on this study, we propose to deliver vibrotactile CR stimulation during a longer treatment period, in order to assess durability and efficacy vs. a sham vibrotactile approach. This study is designed to best assess vibrotactile CR stimulation compared to sham as an alternative to best medical therapy for Parkinson's disease. With our

project, we are hoping to establish a simple, non-invasive treatment that will provide ongoing relief with minimal side effects or inconvenience to the patient.

#### Sham control

Parkinson's patients are particularly vulnerable to the placebo effect. The best method of reducing placebo effects in a placebo effect prone population is to blind the participants. In order to do this, sham participants will receive a non-stimulation (0 amplitude) chip that is inserted into the vibrotactile device. All participants will be told that they will receive 1 of two chips, 1 is regular vibrotactile reset and the other (sham) is called Stochastic resonance vibrotactile coordinated reset. The patient will learn that Stochastic resonance treatment is most effective when the patients vibratory stimulus threshold (i.e the minimum perception thresholds) is set as 90%. This means that the patient should not feel the vibrations on their fingers if they receive vibratory stochastic resonance. We will take vibrotactile threshold measurements from patients to make this story convincing and to add another dependent measure. If placed into the sham condition, the patient will receive no stimulation, however they will be convinced that they are receiving stimulation

Vibrotactile CR stimulation therapy system is a commercially available (though not yet FDA-approved), non-invasive, battery-operated mobile device. The device consists of a handheld component with vibro-tactile stimulators (tactors) and is fitted and programmed by a qualified healthcare professional familiar with Parkinson's disease treatment (e.g., physicians, advanced practice providers, nurses and/or their clinical research assistants).

Several brain diseases are characterized by abnormal neuronal synchronization. CR stimulation was developed to specifically counteract neuronal synchronization (Tass 2003). CR stimulation is a spatio-temporally patterned desynchronizing stimulation technique. According to computational studies CR stimulation induces a reduction of the rate of coincidences and, mediated by synaptic plasticity, an unlearning of abnormal synaptic connectivity (Tass & Majtanik 2006). A sustained desynchronization is achieved by shifting the neuronal system from a pathological to a physiological attractor (Tass & Majtanik 2006). It was shown computationally that CR is effective regardless of whether it is delivered directly to neuronal somata or indirectly via excitatory or inhibitory synapses (Popovych & Tass 2012). Accordingly, it was hypothesized that CR stimulation can be realized using both invasive and non-invasive stimulation modalities (Popovych & Tass 2012).

In accordance with theoretical predictions, electrical deep brain CR stimulation has pronounced therapeutic after-effects in Parkinsonian monkeys (Tass et al., 2012a) as well as cumulative and lasting therapeutic and desynchronizing after-effects in Parkinsonian patients (Adamchic et al., 2014a).

In patients with tinnitus, acoustic CR stimulation leads to a significant clinical improvement (Tass et al., 2012b) as well as a decrease of pathological neuronal synchrony in a tinnitus-related network of auditory and non-auditory brain areas (Tass et

al., 2012b; Adamchic et al., 2014b( along with a normalization of tinnitus characteristic abnormal interactions between different brain areas (Silchenko et al., 2013; Adamchic et al., 2014c).

The somatosensory neuronal response to vibratory stimuli [Weiss et al., 2009] provides a dynamic stimulus response characteristics required to robustly deliver CR stimulation [Tass 2017]. As abnormal neuronal synchrony appears to play a major role in Parkinson's disease [Hammond et al., 2007], desynchronization of abnormal synchrony represents a possible target for intervention in Parkinson's patients. It was therefore hypothesized that vibratory CR stimulation might cause a desynchronization of abnormal neuronal synchrony in Parkinson's disease patients and, in turn, induce a decrease of abnormal synaptic connectivity, ultimately giving rise to a sustained relief of symptoms [Tass 2017]. In a first-in-human study in five subjects with idiopathic Parkinson's disease tolerability and feasibility of vibrotactile CR stimulation therapy was demonstrated [Syrkin-Nikolau et al., 2018]. Subjects received 2x2-hour vibrotactile CR stimulation per day during three consecutive days. The CR treatment caused significant effects on gait and bradykinesia, as shown by off medication kinematic assessments during the three treatment days as well as at a one-week and a four-week follow up visit [Syrkin-Nikolau et al., 2018].

#### Primary Hypothesis

Vibrotactile CR stimulation is not expected to cause discomfort or pain in patients as confirmed in a prior study with Parkinson's disease (IRB# 45096; Syrkin-Nikolau et al., 2018). It is expected to lead to a decrease in severity of motor symptoms from baseline to 6 months, as measured by the Movement Disorders Society's Unified Parkinson's Disease Rating scale (MDS-UPDRS) part III and patient motor diaries to capture mean time when patients' medications have worn off and are not controlling symptoms (OFF time), time when patients' medications are working effectively to control symptoms (ON time), ON time with troublesome dyskinesia, and sleep time – all factors which can be affected by Parkinson's disease. As secondary endpoints, we expect this may result in the patient's ability to reduce reliance upon dopaminergic medications, therefore we will measure changes in levodopa dose equivalency. Additionally, we will assess for improvement in non-motor symptoms of Parkinson's disease, ability to perform activities of daily living and reduction in dyskinesia, which will be measured by the Movement Disorders Society's Unified Parkinson's Disease Rating scale (MDS-UPDRS), parts 1, 2 and 4 and the Schwab and England Activities of Daily Living score. We expect patient quality of life will increase after stimulation, which will be measured by the Parkinson's Disease Questionnaire-39 (PDQ-39) scale. To get a general sense of symptom change, we will assess the patient and clinician Global Rating of Change (GRC) scale and the Patient Global Impression of Change. We will also asses speech using comprehensive speech evaluations. We predict that this decrease in symptoms will be apparent within 1 month of vibrotactile stimulation and that this treatment will be durable as assessed up to 1-months post-stimulation.

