## Statistical Analysis

Our primary hypothesis is that vibrotactile CR stimulation (i) will improve the outcome measured as On-time at least by 30% compared to the baseline after three months of usage. We also expect that (ii) the relative increase in On-time in the intervention arm (using vibrotactile CR stimulation) will be at least 20% compared to the control arm (Sham) after three months of usage. In order to test these hypotheses, we will perform Welch's t-test (paired t-test for the first hypothesis and unpaired two-sample t-test for the second hypothesis). Our power analysis shows that the sample size of 10 patients for each arm will provide 85% - 98% of power for detecting statistically significant difference based on the mean On Time of 7.3 at baseline and SD of 2-2.5 that were obtained from our preliminary study.

**Based on this power analysis, we are planning to enroll a minimum of 60 patients. 30 patients will be randomized to receive the real stimulation initially. The remaining 30 will be randomized to receive sham stimulation, using dedicated sham stimulation pattern.**

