#### Benefits

The patient's Parkinson's disease symptoms may be reduced, and quality of life may be increased, as a result of the vibratory stimulation, either for a transient period of time such as a few hours post-stimulation, or possibly even for several weeks to months. Ultimately, this pilot study could provide evidence that vibro-tactile stimulation is a safe and effective method to treat symptoms of Parkinson's disease, which would provide a much-needed alternative to medication, surgery and other invasive procedures in the future.

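### The two primary hypotheses differ, and the Statistical Analysis section puts the primary label on a before-after test in the CR arm rather than on CR versus sham

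*Combined protocol and SAP*

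**What the plan says.** Two sections of the combined protocol and SAP state a primary hypothesis.

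- **Primary Hypothesis section.** It opens with tolerability, then expects a "decrease in severity of motor symptoms from baseline to 6 months". The measures listed before the text turns to secondary endpoints are MDS-UPDRS III and diary OFF time, ON time, ON time with troublesome dyskinesia, and sleep time. Sham is not mentioned, and no test is named.
- **Statistical Analysis section.** The primary hypothesis here is that (i) CR "will improve the outcome measured as On-time at least by 30% compared to the baseline after three months of usage", tested by a paired t-test. A further expectation follows: (ii) that "the relative increase in On-time in the intervention arm (using vibrotactile CR stimulation) will be at least 20% compared to the control arm" at three months, tested by an unpaired two-sample t-test. One power statement covers both: a "sample size of 10 patients for each arm will provide 85% - 98% of power", from a baseline mean of 7.3 and an SD of 2–2.5. The plan is then to enroll at least 60 patients, 30 per arm.

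The stated reason for the design, in the Background, is to treat for longer "in order to assess durability and efficacy vs. a sham vibrotactile approach". The Sham control section warns that Parkinson's "patients are particularly vulnerable to the placebo effect". No section gives a significance level, sidedness, an order of testing, or a rule for combining (i) and (ii).

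**The concern.** The two sections differ in measures, time point and contrast. On-time is common to both, but at month 6 in one and month 3 in the other. MDS-UPDRS III and month 6 have no named test.

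The more serious problem is which test carries the label. Test (i) uses only the CR arm. It cannot separate a CR effect from placebo response, regression to the mean or a change in medication, and the protocol itself expects placebo response. A team following the Statistical Analysis section literally could report a significant rise in the CR arm as the primary result even if sham patients rose just as much. That would not answer the question for which patients are randomized to sham.

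**Working it through.** **Inputs from the Statistical Analysis section:** baseline mean 7.3; SD 2–2.5; 10 per arm in the power statement; 30 per arm planned; effects of 30% within arm and 20% versus sham.

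**Assumptions, because the documents are silent:** 5% level, two-sided unless stated; null hypothesis of no change or no difference; the SD is that of the quantity analysed (for test (i), the change). The size of the placebo response is not given, so a range is shown.

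**1. Reproducing the stated 85%–98% at 10 per arm**

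Test (i): difference 0.30 × 7.3 = 2.19. One-sided normal power is Φ(2.19/SD × √10 − 1.645).

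- SD 2.5: Φ(2.770 − 1.645) = 87.0%
- SD 2: Φ(3.463 − 1.645) = 96.5%

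This is close to the stated range. Other versions of test (i) fit less well: one-sided t 82%/94%, two-sided normal 79%/93%, two-sided t 69%/87%.

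Test (ii): the base of the 20% is not stated, so three readings were tried.

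- 20% of baseline: 0.20 × 7.3 = 1.46
- CR mean 20% above sham, with CR at 7.3 × 1.3 = 9.49: 9.49 − 9.49/1.2 = 1.58
- 20% of 9.49: 1.90

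Power is from the noncentral t with noncentrality (difference/SD) × √(n/2) and 2n − 2 degrees of freedom, two-sided 5%, for SD 2.5 to 2:

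| Difference | 10 per arm | 30 per arm |
|---|---|---|
| 1.46 | 24%–34% | 60%–79% |
| 1.58 | 27%–39% | 67%–85% |
| 1.90 | 36%–52% | 82%–95% |

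The most favourable version tried at 10 per arm (1.90, one-sided normal) gives 52%–68%. So the stated range roughly fits test (i) and does not reproduce for CR versus sham.

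**2. Test (i) when CR has no effect beyond sham**

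Let both arms improve by the same amount through placebo response. With 30 in the CR arm the paired t-test has noncentrality (change/SD) × √30 and 29 degrees of freedom.

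| Shared change | Hours (× 7.3) | Noncentrality, SD 2.5 / 2 | Test (i) significant | CR–sham test significant |
|---|---|---|---|---|
| 5% | 0.365 | 0.80 / 1.00 | 12%–16% | about 5% |
| 10% | 0.73 | 1.60 / 2.00 | 34%–49% | about 5% |
| 20% | 1.46 | 3.20 / 4.00 | 87%–97% | about 5% |

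The last column stays at the nominal level because the shared change cancels between arms.

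**3. Counting success on either (i) or (ii), with no placebo change**

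Simulation with 30 per arm gives about 8% when (ii) is run on change scores and 9%–10% when it is run on raw month-3 values. Two independent tests would give 1 − 0.95² = 9.75%. This is small beside step 2.

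**The case against.** **The study calls itself exploratory.** The page with the Investigator's Agreement says: "The purpose of the study is to verify the safety and tolerability of non-painful sensory (tactile) vibratory stimulation". The Benefits section says "this pilot study could provide evidence that vibro-tactile stimulation is a safe and effective method". Strict error control is a confirmatory standard. This stands in part and lowers the severity. But the plan still randomizes 60 patients to CR or sham, names significance tests and claims power, so it should say which comparison answers the efficacy question. The safety purpose adds another candidate primary aim; it does not settle the choice.

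**The Statistical Analysis section may govern.** It is the only place that names tests, and month 3 lies inside the six-month window. That is a reasonable reading, though no text says so. It would resolve the conflict between sections but leave the primary label on the uncontrolled test.

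**Both tests might have to succeed.** That would remove the inflation in step 3 and protect against step 2. No such rule is written.

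**Stronger readings that the documents do not support.**

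- A reader might infer that the plan does not rank (i) and (ii) at all. Its wording does: the primary label goes with (i), and (ii) follows as an added expectation. The fault is where the label sits.
- A reader might infer that the sham comparison is missing. It is planned, with a named test.
- A reader might infer a larger multiplicity figure by counting month-6 tests of MDS-UPDRS III and each diary category against sham. No section plans those tests, and the diary categories share the same day, so treating them as independent would not be justified.
- A reader might infer that 30 per arm is too few. Step 1 gives anything from 60% to 95%, depending on readings that the plan leaves open. Analysis of change scores could also do better than shown. Reaching 85% at 10 per arm that way would need an unstated correlation with baseline of about 0.86–0.92 at SD 2.5, or 0.78–0.87 at SD 2.

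**Conclusion.** The concern holds. The plan has two non-matching primary hypotheses and no alpha, sidedness, order or combination rule. The section that names the tests labels a within-arm change as primary although the aim is efficacy against sham. The main risk is a positive primary result produced by placebo response. Its probability depends on a placebo size that the documents do not give, together with the assumed 5% two-sided level and an SD of change of 2 to 2.5. The multiplicity between (i) and (ii) is secondary, and its 8%–10% applies only if either success would count. The power statement is not tied to a hypothesis and gives no reproducible support to the CR–sham comparison; whether the planned size is adequate cannot be decided from the text. This should be corrected before unblinding. The pilot and exploratory wording limits how much weight the trial's answer can bear, but a literal reading can still give the wrong answer.

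**What to change.** Before unblinding, rewrite the Primary Hypothesis and Statistical Analysis sections so that they name the same single primary test: a CR–sham comparison of one endpoint at one time point, with alpha and sidedness. The choice of endpoint is the sponsor's. On-time at month 3 is one candidate, because its test is already named. Move within-arm test (i) and all other measures and time points to secondary.

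Then restate power for that test at 30 per arm, saying what the 20% is a percentage of and whether the SD of 2–2.5 is of raw values or of change.

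The cost is new wording in two sections and one recalculation; no visit or assessment changes. The sponsor gives up the option of several primary endpoints, and the restated power may be less favourable than 85%–98%.

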## Relevance

If the results of this study suggest that vibrotactile CR stimulation is safe and effective for the treatment of Parkinson's disease, this non-invasive treatment approach would have a substantial impact on Parkinson's disease.

## Patient Population

Patients presenting Parkinson's disease as identified by Stanford physicians in clinic, will be eligible for participation in this study. Patients will be screened and selected from the population of people with Parkinson's disease who are routinely seen in the Stanford Neuroscience Clinic. It should be emphasized that patients will be allowed to continue any oral medications once stimulation is initiated for their Parkinson's disease symptoms. The doctor and/or research coordinator may introduce the study to potential candidates in-person at Stanford's Neuroscience Clinic, and the research coordinator can also contact potential candidates by the phone after the doctor's referral.

## Study Sites

The Stanford University Medical Center will be the Coordinating Center for this study. Stanford's Neuroscience Outpatient Clinic will be used for study visits and assessments.

## Inclusion Criteria

- 1) Age 18 and older
- 2) Diagnosis of idiopathic Parkinson's disease.
- 3) Levodopa responsiveness as defined by at least a 30% reduction in MDS-UPDRS motor subscale (excluding tremor scores) in the ON vs OFF medication state.
- 4) Willing to participate in the vibrotactile stimulation sessions for 2 consecutive days initially and willing to return for follow-up visits
- 5) Able to provide informed consent.
- 6) Appropriate social support

## Exclusion Criteria

- 1) Hoehn and Yahr stage greater than 3 in the on medication state
- 2) Presence of other forms of non-idiopathic parkinsonism, including but not limited to atypical parkinsonism, medication induced parkinsonism, vascular Parkinsonism
- 3) Any illness that in the investigator's opinion precludes participation in the study
- 4) Subjects unable to communicate with the investigator and staff

## Study Procedures

Once the participant has given informed consent and after baseline screening, the participant will be enrolled in the study and will come to Stanford for 4 visits, each visit being 2 consecutive days. Participants will undergo a series of motor evaluations, speech assessments and EEGs. Participants will be enrolled in the study for 7 months. They will receive treatment for 6 months and no treatment for 1 month. Patients will return for follow up visits every 3 months up until the 6 month follow up. After the 6

[figure not shown]
month follow up the patient will go off stimulation for 1 month and return for the 7 month follow up to assess long term effects. Data will be accessed only by Stanford researchers on-site

PD-related brain oscillations will also be assessed by high density (256-channel; Geodesic EEG system, EGI Electrical Geodesics, Inc. EEG recordings. Acute effects of stimulation as well as acute after-effects of stimulation on the power of cortical currents in different brain areas as well as on phase amplitude coupling between different brain oscillations will be studied with methods as in [I. Adamchic, B. Langguth, C. Hauptmann, P.A. Tass: Abnormal brain activity and cross-frequency coupling in the tinnitus network. *Frontiers in Neuroscience* 8 (2014) 284; I. Adamchic, T. Toth, C. Hauptmann, H. Meister, M. Walger, B. Langguth, I. Klingmann, P.A. Tass: Auditory coordinated reset stimulation has a specific desynchronizing effect on tinnitus related oscillatory brain activity. *Neuroimage: Clinical* 15 (2017) 541-558]. EEG is expected to also provide further objective parameters. Moreover, EEG markers may enable predictions of long-term stimulation effects by correlating acute electrophysiological effects and after-effects with long-term clinical (and electrophysiological) effects of stimulation. We anticipate to correlate changes of neural synchrony in different brain areas with different changes of motor, cognitive, somatosensory, and visual symptoms. Particular stimulation parameters may differentially affect different symptoms. Because of this, there may be changes of the finger representation in the somatosensory cortex over time.

Thus, future optimization may be possible by individually calibrating (personalizing) stimulation based on biomarkers. This will be the subject of a future study, but we will leverage the opportunity the proposed study provides to collect this electrographic data. We anticipate that vibrotactile CR counteracts PD-related patterns of EEG power (i.e. synchrony) and effective connectivity.

After being trained on how to use the device and administer the traditional physical exams and assessments by the study investigators, the PI's clinical staff will apply the device therapy, monitor the participant through the sessions to ensure patient comfort and proper device function, and perform the assessments instructed. [name] will lead the training of all key personnel on the use of the E-3 vibrotactile stimulator and the protocol will be discussed during an in-service for all research personnel involved in the study to ensure that everyone understands the protocol prior to participating in any research activity. A patent for vibrotactile CR stimulation is filed and owned by Stanford University. Inventor is [name] who will provide as needed consultation to this study at no fee. Stanford Office of Technology and Licensing is actively setting up an industrial collaboration for this treatment of Parkinson's disease.

The vibrotactile stimulator will be attached gently to the fingers (thumb excluded) bilaterally using a glove with an elastic band a Velcro strip or a similar method. When the stimulation is activated, the stimulators will apply gentle vibration to the different fingers sequentially. (**Figure 1**)

Approximately one week later (Day 7 – this will be an optional visit for as needed training) and four weeks later (Day 28), the participant will return for follow-up physical examinations and assessments only, again occurring at the Stanford Outpatient Neuroscience clinic. These visits will last approximately two hours.

*Figure 1: Vibro-Tactile System integrated into glove*

